8.4 Attainment of Steady State

For Part 2, a repeated measures analysis will be carried out on natural log-transformed pre-dose concentrations (Days 9 to 12) to determine attainment of steady-state for ATH-399A. The approach is based on the comparison of natural log-transformed trough concentration values. The response variable will be the natural log-transformed pre-dose concentration and the model will include dose, visit, and dose-by-visit interaction as fixed effects and participant within dose as repeated effect. The model will be fit using restricted maximum likelihood and the Kenward-Roger degrees of freedom approximation.^b An unstructured covariance matrix will be used; if the unstructured covariance matrix fails to converge, simpler covariance matrix structures such as compound symmetry will be considered.^c

This document is confidential.

The SAS code will follow the format below. The input variables, datasets, and labels are depicted in italicized red text and have been given generic names.

```
proc mixed data=dataset;
  class dose visit participant;
  model ln_ctrough = dose visit dose*visit / ddfm=KR;
  repeated / type=un subject=participant(dose);
  lsmeans dose*visit;
run;
```

Contrasts will be tested between each dosing timepoint and the pooled mean over all outstanding dosing timepoints (i.e., Day 9 pre-dose value versus the average pre-dose value of Days 10 through 12, Day 10 pre-dose value versus the average pre-dose value of Days 11 through 12, Day 11 pre-dose value versus the pre-dose value of Day 12).

The first non-significant comparison will be concluded to be the dose number (Day x) at which steady state concentrations are attained. If the dose*time effect is found statistically significant, these contrasts will be done separately for each dose level. The p-value for difference of least-squares means (LSM) will be provided.

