5.2 Study Rationale

The study design meets the objectives of pharmacokinetic profile and food effect assessments and the evaluation of safety, tolerability and exposure profile resulting from single and multiple dose administration, required in Phase 1 studies. Part 2 will initially evaluate the safety of multiple doses in participants aged 18 – 55 years. Once safety is established, the study will evaluate dosing in healthy participants of either gender in the >55-80 year age range to match the approximate age range of the target PD population. A typical crossover design is adopted for the evaluation of food effect. The single and multiple ascending dose stages are randomized, double-blind, and placebo-controlled. The number of participants is based on standard practices of clinical pharmacology and clinical development.

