Blood samples for PK will be collected pre-dose and at specified time points up to 96 hours post-Day 12 dose. Vital signs, ECG, telemetry, safety lab (including drug screen, cotinine, and alcohol breath test), C-SSRS, and physical and neurologic examinations will be performed at specified times. AEs will be recorded throughout the study. For details regarding the timing of specific procedures see [Table 3](#).

Additional Cohort: Following assessment of MAD dosing in participants, an additional cohort of approximately 8 participants will be evaluated at a dose level determined to be safe by the SRC. After assessing eligibility during the 4-week screening period, 8 participants (approximately equal numbers of males and females, with a minimum of 2 of each gender), aged >55-80 years, inclusive, will be enrolled. The study drug will be administered once daily (QD) in the fasted state for a total of twelve (12) consecutive days. On Days 1 and 12, participants will fast for a minimum of 10 hours prior to dosing and 4 hours following dosing. From Days 2 to 11, participants will fast for a minimum of 2 hours prior to dosing and 2 hours following dosing. Six participants will receive ATH-399A and 2 participants will receive placebo once daily (QD).

Eligible participants in this additional cohort will come to the clinical unit on the day before the first study drug administration (Day -1), for baseline assessments and to confirm eligibility and will stay in the clinical unit for 14 days (13 nights), from Day -1 until Day 13.

Blood samples for PK will be collected pre-dose and at specified time points up to 96 hours post-Day 12 dose. Vital signs, ECG, telemetry, safety lab (including drug screen, cotinine, and alcohol breath test), C-SSRS, and physical and neurologic examinations will be performed at specified times. Adverse events will be recorded throughout the study. Participants will return to the clinical unit for outpatient PK blood sample collections on Day 15 (72 hours post-last dose), and Day 16 (96 hours post-last dose) as well as an outpatient follow-up visit that will take place 7 days after receiving the last dose of study drug, on Day 19 (between Day 19 and Day 22). For details regarding the timing of specific procedures see [Table 3](#).

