3.3.3 Part 2 (MAD)

Participants allocated to the MAD part will receive daily doses of ATH-399A, or matching placebo, under fasting conditions, for 12 consecutive days. The planned dose levels and regimens are listed below in Table 3.3-2.

Table 3.3-2: MAD Treatments

Cohort Number	Number of Participants Receiving ATH-399A	Number of Participants Receiving Placebo	Planned Dose
1	6	2	TBD mg
2	6	2	TBD mg
3	6	2	TBD mg

Each cohort will include 8 participants, 6 participants will receive ATH-399A and 2 participants will receive placebo.

Dose levels of ATH-399A will be based on data from Part 1 (Part 1a and 1b) and recommendation from the SRC. From Day 1 to Day 12, participants will receive either ATH-399A or placebo once daily (QD) for a total of twelve (12) consecutive days.

This document is confidential.

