8.5 Analysis of Accumulation Ratio

For Part 2, an ANOVA model will be used to explore the degree of accumulation after repeated dosing by comparing natural log-transformed AUC on Day 12 ($AUC_{0-\tau}$) with Day 1 (AUC_{0-24}), natural log-transformed C_{max} on Day 12 ($C_{max\ ss}$) with Day 1 (C_{max}), and also to compare untransformed T_{max} on Day 12 ($T_{max\ ss}$) with Day 1 (T_{max}). For each PK parameter, statistical comparisons will be performed across the visits (Day 1 and 12). The estimated ratio (Day 12/Day 1) of model-adjusted geometric means will be used to perform this comparison for AUC and C_{max} .

To estimate the geometric mean ratio, a linear mixed effects model will be fit to the data. The response variable will be the natural log-transformed PK parameter, and the model will include dose, visit, and dose-by-visit interaction as fixed effects and participant within dose as random effect. The model will be fit using restricted maximum likelihood and the Kenward-Roger degrees of freedom approximation.^b

From this model, the difference in means will be estimated for Day 12 versus Day 1 per dose, accompanied by a corresponding (two-sided) 90% CI. The point estimate and confidence endpoints will be exponentiated using base e in order to obtain a point and interval estimate for the ratio of geometric means. These transformed CIs will indicate the degree of accumulation across Day 12 versus Day 1 at each dose, and for each PK parameter. Furthermore, the p-values of overall F tests for dose, visit, and dose-by-visit interaction effects will be reported to four decimal places.

This document is confidential.

The SAS code to fit the model will follow the format below (using the Mixed Procedure). The input variables, datasets, and labels are depicted in italicized red text and have been given generic names.

```
proc mixed data= dataset order= data;
  class participant dose visit;
  model ln_PK_parameter = dose|visit / ddfm= kr solution;
  random participant(dose);
  estimate 'TBD mg Day 12 vs Day 1' visit -1 1
    dose*visit -1 1
      0 0
      0 0 / cl alpha= 0.1;
  /* etc... */
  ods output estimates= estimates tests3= tests;
run;
```

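### SAP 8.4 gives one steady-state day for all Part 2 dose levels unless a low-power dose-by-visit test is significant; per-cohort trough ratios with 90% CIs should be reported whatever that test shows

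*SAP*

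**What the plan says.** SAP 8.4 fits a repeated-measures model to log troughs from Days 9, 10, 11 and 12, with dose, visit and their interaction as fixed effects and an unstructured covariance matrix (simpler structures if it fails to converge). Three contrasts follow: Day 9 against the mean of Days 10-12, Day 10 against the mean of Days 11-12, and Day 11 against Day 12. The decision rule is: "The first non-significant comparison will be concluded to be the dose number (Day x) at which steady state concentrations are attained".

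The contrasts are run by dose level only on a condition: "If the dose*time effect is found statistically significant, these contrasts will be done separately for each dose level". The section states no alpha for this test or for the contrasts, and no limit for a negligible difference.

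On size, SAP 3.3.3 says: "Each cohort will include 8 participants, 6 participants will receive ATH-399A and 2 participants will receive placebo". Table 3.3-2 lists three cohorts with doses to be decided. Protocol 7.1.3 adds that "an additional cohort of approximately 8 participants will be evaluated at a dose level determined to be safe by the SRC", so the >55-80 year cohort may repeat a dose already given to younger participants.

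SAP 8.5 uses the same fixed effects for accumulation and reports by dose unconditionally: "From this model, the difference in means will be estimated for Day 12 versus Day 1 per dose, accompanied by a corresponding (two-sided) 90% CI".

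**The concern.** The condition is a preliminary test. If the interaction is not significant, the plan treats the trough time course as common to all dose levels and reads one steady-state day from the average. With 6 active participants per cohort and no power calculation (SAP 3.2), non-significance says little about whether the time courses agree.

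Pooling also weakens the signal. A rise confined to one of three cohorts enters the pooled contrast at one third of its size, while the standard error falls only by √3. The standardised signal is therefore √3/3 = 0.58 of that cohort's own.

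At stake is how each cohort's Day 12 results are read, since several of them (AUC over the dosing interval, Cmax and Tmax at steady state) carry a steady-state label. A cohort still accumulating could be reported under the pooled day, with no formal cohort-level contrast to show otherwise. The >55-80 year cohort has a specific purpose ("the study will evaluate dosing in healthy participants of either gender in the >55-80 year age range to match the approximate age range"; patients with Parkinson's disease are meant), so its own answer is of interest.

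**Working it through.** The plan gives no power or alpha for SAP 8.4, so there is no figure to reproduce. The rule was simulated instead.

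**Inputs from the documents.** Three cohorts of 6 active participants; four troughs (Days 9-12); the three contrasts and the decision rule above.

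**Assumptions.** Within-participant CV 15-30% with independent residuals, two-sided alpha 0.05, complete data, three distinct doses, two cohorts flat and one slow.

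**Shape of the slow cohort.** Under linear accumulation with once-daily dosing and half-life h hours, the trough after k doses, as a fraction of steady state, is 1 − 2^(−24k/h). The Day 9 trough follows k = 8 doses and the Day 12 trough k = 11.

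| Half-life | Day 9 fraction | Day 12 fraction | Rise, Day 9 to 12 |
|---|---|---|---|
| 48 h | 1 − 2^(−4) = 0.938 | 1 − 2^(−5.5) = 0.978 | 4.3% |
| 96 h | 1 − 2^(−2) = 0.750 | 1 − 2^(−2.75) = 0.851 | 13.5% |
| 120 h | 0.670 | 0.782 | 16.7% |
| 168 h | 0.547 | 0.664 | 21.3% |

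The ceiling for very long half-lives is 11/8 = 1.375, a 37.5% rise. A modest rise inside the window can go with a real shortfall: at 168 h the Day 12 trough is about 66% of steady state.

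**Power of the interaction test.** It has (3 − 1) × (4 − 1) = 6 numerator degrees of freedom. Wilks' lambda (exact F on 6 and 26 df) served as the balanced-data counterpart of the unstructured model; simulated size was 5%.

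- Half-life of 4 to 7 days in one cohort, CV 15-30%: missed in 82% (168 h, CV 15%) to 94% (96 h, CV 30%) of trials.
- At CV 20%: missed in 91% (120 h) and 88% (168 h).
- At 168 h and CV 20%, a Hotelling-Lawley version also gives 88%, compound symmetry 86%, and alpha 0.10 gives 80%.
- Even a rise of 10% per day (1.1³ = 1.33, close to the ceiling) is missed in 62% / 78% / 88% at CV 15% / 20% / 30%.
- At CV 10% the test is better: 62% missed at 168 h and 48% at 240 h.

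When the difference is missed at 168 h and CV 20%, the pooled contrast gives Day 9 to everyone in 88% of those trials. In the other 12% the slow cohort makes the pooled contrast significant and the flat cohorts receive a later day.

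**Does dropping the condition alone cure it?** This is how often the slow cohort is called steady at Day 9 (CV 20%):

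| Truth | SAP rule | Always per cohort, first-non-significant rule kept |
|---|---|---|
| One cohort slow, 120 h | 87% | 80% |
| One cohort slow, 168 h | 83% | 73% |
| All cohorts slow, 120 h | 53% | 80% |
| All cohorts slow, 168 h | 36% | 73% |

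It does not: the gain is small when one cohort is slow, and the loss is large when all are.

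**What an interval would show.** The 90% CI half-width for the Day 9 contrast, as a fold factor, is exp(t × s × √((4/3)/n)), with s = √ln(1 + CV²) and t = 1.753 (15 df). At CV 20%, s = 0.198.

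- Per cohort (n = 6): exp(1.753 × 0.198 × 0.471) = 1.18.
- Pooled (n = 18): exp(1.753 × 0.198 × 0.272) = 1.10.
- On the log scale the ratio of widths is √(18/6) = 1.73.

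At 168 h, the slow cohort's expected Day 9 ratio is exp[ln 0.547 − mean(ln 0.590, ln 0.629, ln 0.664)] = 0.87. Its typical 90% CI is 0.87/1.18 to 0.87 × 1.18, or 0.74 to 1.03. The pooled ratio would be 0.87^(1/3) = 0.95. The cohort interval includes 1, so a test would pass it, but the estimate and lower limit show that steady state is not established.

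**The case against.** Several points on the other side stand.

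- **The kinetics may be fast.** Protocol 9.7 spaces possible Part 2 sentinels by at least 96 hours so that they can be assessed at steady state, and the Part 1b washout starts from 7 days. At a 48 h half-life the rise is 4.3% and nothing of substance is hidden.
- **A common time course is a fair default.** With linear kinetics and similar clearance, time to steady state does not depend on dose, and the pooled contrast is then the sharper tool. The all-slow rows above confirm it.
- **Cohort-level data will exist.** The SAP code prints dose-by-visit means unconditionally, troughs are presented (SAP 8.2.3), and concentrations are summarised by treatment and timepoint (SAP 8). A reader might infer that a slow cohort would be invisible. It would not be; what is missing is a formal ratio with an interval.
- **Little depends on the result.** No parameter or decision in the SAP is conditioned on 8.4, time to steady state is not a listed endpoint, and the primary endpoints are safety.

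A reader might also infer three stronger claims that the documents do not support. First, that the >55-80 year cohort accumulates more slowly: the protocol says only that its age range matches the target population. Second, that 8.4 and 8.5 contradict each other: one tests a time point and the other estimates a magnitude, so 8.5 is a useful pattern rather than a conflicting rule. Third, that per-dose testing should replace pooling, which the simulation argues against.

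**Conclusion.** The point holds as a low-cost improvement. SAP 8.4 lets a low-power test decide whether any cohort-level steady-state contrast is produced. With one cohort at a half-life of 4 to 7 days, that test misses the difference in about 82-94% of trials at within-participant CV 15-30%. The effect is negligible if the half-life is about 48 h or less in every cohort.

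The size rests on assumed CVs, half-lives and alpha, none of which the documents supply, and on three distinct doses with complete data. The documents do not support saying that the Part 2 steady-state conclusion will be wrong. They support saying that a non-significant interaction cannot show that the cohorts agree.

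The condition is also only part of the weakness. Reading non-significance as attainment fails more often still with 6 participants, so the remedy is estimation by cohort alongside the pooled analysis.

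**What to change.** In SAP 8.4:

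1. Keep the three pooled contrasts and report the interaction p-value. Do not demote the pooled contrasts to supportive status.
2. In addition, regardless of that p-value, estimate the same three contrasts for each Part 2 cohort, back-transformed to geometric mean ratios with two-sided 90% CIs, and add the matching ESTIMATE statements on the pattern of 8.5.
3. Use cohort instead of dose as the class factor. If the >55-80 year cohort repeats a dose, a dose factor would merge it with younger participants and no contrast could separate them.
4. State that any conclusion on steady state for a single cohort is drawn from its ratio and CI, and that the first-non-significant rule is not applied to single cohorts.

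The cost is SAP wording and a few lines of code, with no new data. The downside is precision: per-cohort intervals are about 1.7 times wider on the log scale (fold factor 1.18 against 1.10 at CV 20%), so a rise common to all cohorts is seen less sharply in each. Keeping the pooled contrast covers that case.

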8.5 Analysis of Accumulation Ratio

For Part 2, an ANOVA model will be used to explore the degree of accumulation after repeated dosing by comparing natural log-transformed AUC on Day 12 ($AUC_{0-\tau}$) with Day 1 (AUC_{0-24}), natural log-transformed C_{max} on Day 12 ($C_{max\ ss}$) with Day 1 (C_{max}), and also to compare untransformed T_{max} on Day 12 ($T_{max\ ss}$) with Day 1 (T_{max}). For each PK parameter, statistical comparisons will be performed across the visits (Day 1 and 12). The estimated ratio (Day 12/Day 1) of model-adjusted geometric means will be used to perform this comparison for AUC and C_{max} .

To estimate the geometric mean ratio, a linear mixed effects model will be fit to the data. The response variable will be the natural log-transformed PK parameter, and the model will include dose, visit, and dose-by-visit interaction as fixed effects and participant within dose as random effect. The model will be fit using restricted maximum likelihood and the Kenward-Roger degrees of freedom approximation.^b

From this model, the difference in means will be estimated for Day 12 versus Day 1 per dose, accompanied by a corresponding (two-sided) 90% CI. The point estimate and confidence endpoints will be exponentiated using base e in order to obtain a point and interval estimate for the ratio of geometric means. These transformed CIs will indicate the degree of accumulation across Day 12 versus Day 1 at each dose, and for each PK parameter. Furthermore, the p-values of overall F tests for dose, visit, and dose-by-visit interaction effects will be reported to four decimal places.

This document is confidential.

The SAS code to fit the model will follow the format below (using the Mixed Procedure). The input variables, datasets, and labels are depicted in italicized red text and have been given generic names.

```
proc mixed data= dataset order= data;
  class participant dose visit;
  model ln_PK_parameter = dose|visit / ddfm= kr solution;
  random participant(dose);
  estimate 'TBD mg Day 12 vs Day 1' visit -1 1
    dose*visit -1 1
      0 0
      0 0 / cl alpha= 0.1;
  /* etc... */
  ods output estimates= estimates tests3= tests;
run;
```

8.6 Assessment of Food Effect

To assess the food effect on ATH-399A exposure in Part 1b, the values of AUC_{0-t} , $AUC_{0-\infty}$, and C_{max} calculated for the two diet regimens (fed and fasted) will be evaluated by ANOVA, with terms for sequence, period, and treatment as fixed effects and participant within sequence as a random effect. The exposure measurements ($AUCs$ and C_{max}) will be natural log-transformed prior to analysis. The model will be fitted using restricted maximum likelihood and the Kenward-Roger degrees of freedom approximation. [Error! Bookmark not defined.](#)

The 90% CI for the ratio of the geometric means for AUC_{0-t} , $AUC_{0-\infty}$, and C_{max} obtained between the fed and fasted conditions will be calculated. The absence of a food effect will be concluded when the 90% CI for the ratio of means (geometric means based on log transformed data) of fed and fasted conditions fall within 80% - 125% for AUC_{0-t} , $AUC_{0-\infty}$, and C_{max} .

The SAS code for the analysis model for ANOVA will follow the format given below (using the Mixed Procedure to fit the linear regression). The input variables, datasets, and labels are depicted in italicized red text and have been given generic names.

```
proc mixed data= dataset;
  class participant treatment sequence period;
  model var = treatment sequence period / solution ddfm= KR;
  random participant(sequence);
  lsmeans treatment / cl alpha= 0.1;
  estimate 'fed vs fasting' treatment 1 -1 / cl alpha= 0.1;
  ods output estimates = estimates covparms = covparms;
run;
```

Intra- and inter-participant CV% will also be estimated.

9. Pharmacodynamic (PD) Analyses

There will be no PD analyses for this study.

This document is confidential.

10. Safety

Safety and tolerability analysis will be performed for all participants in the safety population. No inferential statistical analysis of safety data is planned. For Parts 1a and 2, summary tables will be presented by dose (study drug and placebo) and by study drug overall. For Part 1b, summary tables will be presented by treatment and overall.

10.1 Administration

Study drug administration will be listed by participant. A listing will also be provided with first participant enrolled date, first participant first dose date, last participant first dose date, first participant exit date, last participant last dose date, and last participant exit date, for each study part and overall.

10.2 Adverse Events (AEs)

AEs will be coded using the latest version of the MedDRA. Output data will include the MedDRA version used in the study. AEs will be grouped by SOC and PT and summarized by actual treatment. The summary tables will present the number and percentage of total participants and number of events by SOC and by PT.

All AE summaries will be restricted to treatment-emergent AEs (TEAEs), defined as AEs that commence on or after the time of first study drug administration. Any AE that first occurs pre-dose but worsens in intensity after the first study drug administration will also be considered a TEAE. AEs without an onset date or time, or AEs with an onset date of the date of first study drug administration but without an onset time, will be defined as treatment-emergent, unless an incomplete date (e.g., month and year) clearly indicates that the event started prior to administration of first study drug, or the AE stop date indicates that the event started and stopped prior to administration of first study drug.

TEAEs will be attributed to the last treatment administered. TEAEs continuing after dosing in the next treatment period will be evaluated on a case-by-case basis.

The number and percentage of participants experiencing TEAEs and the number of TEAEs will be tabulated. Participants who experience the same TEAE (in terms of MedDRA PT) more than once will only be counted once per treatment or period, however, the total number of events will be counted per category. This also applies to sub-categories displayed in the summaries.

The following summaries will be presented:

- Overall summary of TEAEs
- TEAEs by SOC and PT
- TEAEs by SOC, PT, and intensity
- TEAEs by SOC, PT, and relationship to study drug
- Serious TEAEs by SOC and PT

The Investigator will make an assessment of intensity for each AE and SAE reported during the study per Common Terminology Criteria for Adverse Events (CTCAE) v5.0 grading criteria:

This document is confidential.

- Grade 1: Mild, asymptomatic or mild symptoms; clinical or diagnostic observations only; treatment not indicated.
- Grade 2: Moderate, minimal, local, or non-invasive treatment indicated; limiting age-appropriate instrumental activities of daily life.
- Grade 3: Severe or medically significant but not immediately life-threatening: hospitalization or prolongation of hospitalization indicated; disabling; limiting self-care activities of daily life.
- Grade 4: Life-threatening consequences; urgent treatment indicated.
- Grade 5: Death related to AE.

The Investigator is obligated to assess the relationship between study treatment and each occurrence of each AE/SAE. The Investigator will use clinical judgment to determine the relationship. All AEs will be assigned a causality attribution as follows:

- Related: There is a reasonable likelihood of a causal relation between study drug and the AE.
- Not related: There is reasonable certainty that the cause of the AE is another etiology such as concomitant medication, disease progressions or other medical conditions and not related to study treatment.

All AEs will be listed. The following listings will be included: Non-TEAEs, TEAEs, and serious AEs.

